#### **5.4.2.4. Bayesian analysis HPX2008**

An exploratory analysis that uses Bayesian methods may be conducted to evaluate VE. The prior to be used for this analysis will be a robust, meta-analytic one based on pre-specified weighting of the external Phase 2b data (study HPX2008/HVTN 705) as informative prior and a non-informative prior. Details of pre-specified weights and priors will be specified in the DPS before doing the analysis after unblinding of HPX3002.

#### **5.4.2.5. Correlates**

If VE is established, an attempt will be made to identify correlates of increased risk of HIV-1 infection, correlates of VE, and best individual-level classifiers of HIV infection, and to assess mediators of vaccine efficacy. To this extent, appropriate statistical methodology will be applied or developed, and will be described in a (separate) SAP for correlate identification. A pre-specified case-control study of immune responses elicited by vaccination in active vaccine recipients may be performed to identify vaccine-induced correlates of protection and/or risk. Both single parameter and combinations of multiple immunologic parameter models will be explored. The presence of time-dependent correlates of protection may be examined in addition to single time point immune responses, including the peak immune response after the primary vaccination series, or the time point most closely preceding the diagnosis of HIV-1 infection. To further ascribe immune correlates of protection and/or specifically of VE, placebo case and control samples may also be included in a secondary stage of analysis.

### **6. IMMUNOGENICITY ANALYSIS**

This section refers to the general analysis of immunogenicity and does not include details on the correlates analysis (separate SAP).

The analysis will be done on a subset of the complete set of participants who were randomized and vaccinated and for whom immunogenicity data are available, excluding participant samples with major protocol deviations expecting to impact the immunogenicity outcomes. Samples obtained after missed doses, incomplete doses or samples obtained after HIV infection will be excluded from the analysis.

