	
safety review team approval of whether the participant can still be vaccinated, although cases should still be notified to the sponsor.
 
Added that in case of out of window study vaccinations there should be an interval of at least 28 days between subsequent study vaccinations.
	
12.3.3 Pregnancy	Clarified that any postnatal sequelae in an infant will be collected if possible.	Clarification upon ethics committee request.
1.1.2 Background on the Study Vaccines REFERENCES	The background section of the protocol has been updated with a summary of the HPX2008/HVTN 705 results.	Update
TIME AND EVENTS SCHEDULE 9.1.5 Post-vaccination Follow-up Phase 10.2 Discontinuation of Study Vaccination/Withdrawal from the Study	Specified that participants who received the first 3 vaccinations but discontinue study vaccination before receiving the 4 th vaccination, should continue with safety, immunogenicity and HIV diagnosis assessments as planned. All other participants who discontinue study vaccination, should continue with safety and HIV diagnosis assessments as planned.	To minimize blood draws and testing for participants not contributing to the per-protocol population to be used for the primary efficacy analysis.
4.3 Prohibitions and Restrictions	Clarified that for surgeries mentioned in exclusion criterion 3, it will be per investigator's judgement whether the surgery would interfere with protocol assessments during the study. The safety review team will be available for consultation, where appropriate.	Clarification

Amendment 5 (19 May 2021)

Overall Rationale for the Amendment: This amendment has been created to provide information and guidance for investigators on signs and symptoms and on medical management should very rare events of thrombosis with thrombocytopenia syndrome (TTS) occur, as observed in another Ad26-based vaccine program (Ad26.COV2.S, COVID-19 vaccine). The Ad26.Mos4.HIV vaccine uses the same Ad26 vector as Ad26.COV2.S, but has different transgene inserts. To date, no cases of TTS have been reported in Janssen's Ad26.Mos4.HIV clinical studies nor in any other Ad26-based non-COVID-19 vaccine programs from Janssen. Nonetheless, TTS will be followed in this protocol as adverse event of special interest (AESI) that needs to be reported to the sponsor within 24 hours of awareness. Additional changes are listed below.

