- h HIV testing should be performed per sponsor approved algorithm, as described in the Study Specific Procedures Binder. To avoid delays in initiation of combined antiretroviral treatment, local HIV PCR testing is allowed only in case of suspected acute HIV infection, in case of recent HIV exposure, or in case a request for sample redraw is received from the central HIV testing laboratory for confirmation of an HIV positive test. Upon discretion of the investigator, additional HIV tests may be performed during unscheduled visits; participants should refrain from performing any HIV testing outside of the study protocol.
- i If a participant becomes HIV 1 infected during the study, no further scheduled vaccinations will be administered. The participant should follow further assessments as outlined in the [Time and Events schedule for participants who become HIV 1 infected](#).
- j The screening HIV test should be performed within 28 days prior to first vaccination.
- k HIV test 13 months post 1st vaccination will be collected but is only to be analyzed in case the test at 15 months is positive and the test at 12 months was negative.
- l The following concomitant therapies must be recorded from the first study vaccination to 1 month after the last study vaccination: analgesics/antipyretic medications and non steroidal anti inflammatory drugs, hormonal therapy, hormone based contraception, systemic corticosteroids, antihistaminics, monoclonal antibodies (mAbs), or vaccinations must be recorded from the first study vaccination to 1 month after the last study vaccination. Exception: COVID 19 vaccination must be recorded as of any time before screening until the end of the study. All other concomitant therapies should also be recorded if administered in conjunction with new or worsening adverse events reported per protocol requirements. If applicable, HIV prevention medication should be recorded.
- m The use of PrEP, PEP, hormonal therapy, hormone based contraception, and all COVID 19 vaccinations should be recorded. All other concomitant therapies should also be recorded if administered in conjunction with new or worsening adverse events reported per protocol requirements.
- n Check clinical status again before first dose of study vaccine.
- o For participants of childbearing potential only.
- p A urine pregnancy test is to be performed every 3 to 6 months.

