Reports include severe cases of venous thrombosis at unusual sites such as cerebral venous sinus thrombosis (CVST), splanchnic vein thrombosis and arterial thrombosis, in combination with thrombocytopenia. Venous thrombosis cases have also been reported at more common sites, eg, in the lower extremities. The onset of associated symptoms has usually been 1 to 4 weeks, but sometimes even later following vaccination (up to 42 days as per the American Society of Hematology 2021²). TTS cases have been reported mostly in women under 60 years of age although some cases of TTS have also been reported in men and in individuals older than 60 years of age. Thrombosis in combination with thrombocytopenia has been fatal in some cases. The exact pathophysiology of TTS is unclear. This event has not been observed to date with any other Janssen Ad26-based vaccines (including with Ad26.Mos4.HIV). Participants should be instructed to seek immediate medical attention if they develop symptoms such as shortness of breath, chest pain, leg pain or leg swelling, persistent abdominal pain, severe or persistent headaches, blurred vision, skin bruising or petechiae beyond the site of vaccination, changes in mental status or the occurrence of seizures.

Knowledge about TTS continues to evolve, and updates will be made as new data become available.

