Vaccination with COVID-19 vaccines that have been either licensed or authorized for emergency use (eg, EUA, EUL, or similar program) must take priority over the study vaccine. The interval between study vaccination and administration of a recombinant viral vectored COVID-19 vaccine or a live attenuated COVID-19 vaccine should be at least 28 days. The interval between study vaccination and administration of other types of COVID-19 vaccines (eg, mRNA vaccines, protein-based vaccines) should be at least 14 days.

Treatment with HIV-related mAbs, whether licensed or investigational, during the study is disallowed.

Chronic or recurrent use of immunomodulators/suppressors, eg, cancer chemotherapeutic agents or systemic corticosteroids, is prohibited (after discussion with the HPX3002/HVTN 706 safety review team) starting from 1 month before the planned administration of the first dose of study vaccine until 1 month after the last vaccination. If participants require these medications, they will be withdrawn from the study vaccine administration (See Section 10.2). Note: Ocular, topical or inhaled steroids are allowed.

For participants who become HIV infected, all ARVs and all concomitant therapies administered in conjunction with new or worsening adverse events reported per protocol requirements should be reported.

The HPX3002/HVTN 706 safety review team must be notified in advance (or as soon as possible thereafter) of any instances in which prohibited therapies are administered.

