### 6.3.2. Immunogenicity against the vector

For the **Ad26 vector neutralization assay** the following statistics will be calculated for the seropositivity endpoint: N, % seropositivity, geometric mean and corresponding 95% CI of the actual values.

Participants profiles of the actual values over time will be graphically presented.

Actual values and fold changes (from baseline) are tabulated and shown as dot plots with dots for participant values, and the corresponding geometric mean and 95% CI per time point for each assay.

Participants profiles of the assays against the insert will be repeated, highlighting participants with pre-existing immunity at baseline against the vectors.

Scatterplots with the seropositivity in the Ad26 vector neutralization assay versus the assays evaluating the vaccine response will be provided for the most important time points. In these scatter-plots the actual values will be shown, even if they are below the LLOQ.

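### SAP Section 6 has no rule for samples drawn after a permitted Ad26-vectored COVID-19 vaccine, so the Ad26 vector summaries in SAP 6.3.2 would include responses that the study product did not cause

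*SAP*

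**What the plan says.** **Shared vector.** The rationale for Amendment 5, in the protocol's summary of changes, states: "The Ad26.Mos4.HIV vaccine uses the same Ad26 vector as Ad26.COV2.S, but has different transgene inserts". The current text of Protocol 1.1.2 agrees. After describing TTS with Ad26.COV2.S it adds: "This event has not been observed to date with any other Janssen Ad26-based vaccines (including with Ad26.Mos4.HIV").

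**Permitted exposure.** Protocol Section 8 gives licensed or authorised COVID-19 vaccines precedence over study doses. It sets the spacing between a study vaccination and a "recombinant viral vectored COVID-19 vaccine or a live attenuated COVID-19 vaccine should be at least 28 days". No vectored product is excluded by name.

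**Recording.** Footnote l of the Time and Events Schedule requires that "COVID 19 vaccination must be recorded as of any time before screening until the end of the study".

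**Sample exclusions.** SAP Section 6 removes samples affected by major protocol deviations expected to influence immunogenicity. It continues: "Samples obtained after missed doses, incomplete doses or samples obtained after HIV infection will be excluded from the analysis". The nearest deviation category in SAP 3.8 is receipt of a treatment that the protocol disallows.

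**Affected outputs.** Protocol 9.3 plans Ad26 seropositivity and titre at baseline and after vaccination, in a subset. SAP 6.3.2 reports percentage seropositive, geometric mean and fold change from baseline, with participant profiles and scatterplots. By SAP 2.1.1, outputs are by vaccine regimen unless stated otherwise. The insert-assay profiles are repeated "highlighting participants with pre-existing immunity at baseline against the vectors". The possible subgroups in SAP 6.3 include baseline Ad26 serostatus but not COVID-19 vaccination. The only COVID-19 provision in the SAP is the labelling of pandemic-related deviations in SAP 3.8.

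**The concern.** A placebo recipient can receive Ad26.COV2.S after Day 1 in full compliance with the protocol and then give a blood sample for the Ad26 neutralisation assay. Any rise in that sample cannot come from the study product. Because the vaccination was allowed, the sample meets none of the exclusion criteria and enters the placebo summary unmarked. The same event in a vaccine recipient adds a second source of anti-Ad26 response to the one from the regimen.

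At stake is the reading of one output: the level of vector immunity by arm and its change from baseline. The placebo arm would show background plus COVID-19 vaccine responses, and a reader of the tables could not separate the two. Exposure before Day 1 is a lesser matter, since it is already reflected in the baseline value.

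**Working it through.** The plan states no figure to reproduce here. The check has three parts: whether the exclusion rule catches the exposure, when the exposure can occur, and how the summaries respond to it.

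**1. Does any rule catch it?**

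| SAP provision | Catches a permitted Ad26.COV2.S dose after Day 1? |
|---|---|
| Missed or incomplete doses (Section 6) | No, unless the participant also missed a study dose |
| HIV infection (Section 6) | No |
| Major deviation expected to affect immunogenicity (Sections 6 and 3.8) | No. A dose inside the 28-day interval might count as disallowed treatment; a dose outside it does not |
| Highlighting in 6.3.2 | No. It concerns immunity at baseline only |
| Subgroups in 6.3 | No |

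**2. When can it happen?** Inputs are the target days in Protocol 9.1.2 (study doses on Days 1, 84, 168 and 364) and the 28-day spacing in Protocol Section 8.

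- Between doses 1 and 2: 1 + 28 = Day 29 to 84 − 28 = Day 56, about four weeks.
- Between doses 2 and 3: 84 + 28 = Day 112 to 168 − 28 = Day 140, about four weeks.
- Between dose 3 and the Month 7 sample: the earliest day is 168 + 28 = Day 196, which is the Month 7 target day, so essentially nothing.
- Between doses 3 and 4: Day 196 to 364 − 28 = Day 336, or 140 days, all before the Month 13 sample (Day 394).
- After dose 4: from 364 + 28 = Day 392, with humoral samples at Months 18, 24 and 30 (Days 546, 728 and 910).

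On schedule, the opening before Month 7 is narrow and the opening afterwards is wide. Visit windows, and study doses delayed in favour of a COVID-19 vaccine, can widen the early openings. The documents do not say which post-vaccination samples will be assayed for Ad26.

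**3. How do the placebo summaries respond?** Every input here is assumed, because the documents give none:

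- c, share of assayed placebo participants given Ad26.COV2.S after Day 1 and before the sample: 5% to 40%
- p0, Ad26 seropositivity without that exposure: 10% to 50%
- s, share of exposed seronegatives who seroconvert: 50% to 90%
- R, titre rise in those exposed: 3-fold or 10-fold, with no change in the others

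Observed seropositivity = p0 + c × s × (1 − p0). Geometric mean fold-rise = R^c, because the mean log rise is c × log R.

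Example: 0.10 + 0.20 × 0.90 × (1 − 0.10) = 0.262.

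| c | Seropositive, p0 = 10%, s = 90% | Seropositive, p0 = 50%, s = 50% | Fold-rise, R = 3 | Fold-rise, R = 10 |
|---|---|---|---|---|
| 5% | 14.05% (+4.05 points) | 51.25% (+1.25) | 1.06 | 1.12 |
| 10% | 18.1% (+8.1) | 52.5% (+2.5) | 1.12 | 1.26 |
| 20% | 26.2% (+16.2) | 55.0% (+5.0) | 1.25 | 1.58 |
| 40% | 42.4% (+32.4) | 60.0% (+10.0) | 1.55 | 2.51 |

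Without exposure the placebo fold-rise would be 1.0. A shift appears at any c above zero. The two seropositivity columns are the extremes of the assumed ranges, since s × (1 − p0) runs from 0.25 to 0.81. At c up to 20%, the inflation is 1.25 to 16.2 points.

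**The case against.** The best reply has four parts.

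*The SAP is silent; it does not state that it keeps these samples.* SAP Section 1 places programming detail in the Data Presentation Specifications, and SAP 2.2.3.2 defers the full immunogenicity analyses to a separate Correlates SAP. Either document could hold a rule, and neither is available here. This stands as a limit. But SAP Section 6 itself sets the sample exclusions, so that is where a reader would expect this one.

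*The placebo arm is a concurrent, blinded control.* While the blind held, uptake of COVID-19 vaccines should have been similar in both arms, so the placebo arm carries that background too. This stands. A reader might infer that vaccine-arm fold-rises can no longer be attributed to the regimen, but that goes too far: within-arm values shift and the contrast may be diluted, but the comparison is not lost. It also means that dropping post-exposure samples answers a somewhat different question from keeping them, so exclusion should not be imposed on the main summary.

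*The insert assays measure something else.* This stands. A reader might infer that the insert-response summaries are contaminated as well. The sponsor states that the inserts differ, and SAP 6.1 directs those assays at the insert or HIV-1 antigens. Any effect would be indirect, through anti-vector immunity, and the documents give no figure for it.

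*No label is made wrong.* This also stands. A reader might infer that the plots misclassify who had vector immunity before doses 2 to 4. The SAP plans no such classification. It highlights baseline immunity, which a later COVID-19 dose cannot change, and every vaccine recipient is scheduled to receive Ad26 at each vaccination visit.

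What the reply leaves untouched is the vector assay itself. A permitted Ad26.COV2.S dose can raise its result, and nothing in the SAP marks or separates that sample.

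**Conclusion.** The point holds for the Ad26 neutralisation summaries in SAP 6.3.2 and no further. It rests on three textual facts: the vector is shared, Ad26-vectored COVID-19 vaccination is permitted during the trial, and SAP Section 6 has no rule for it. It also assumes that no document outside this review supplies one.

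The effect is clearest in the placebo arm and more plausible for samples after Month 7. Its size cannot be known from the documents; the 1.25 to 32.4 points in the table show sensitivity to assumptions and are not estimates.

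The consequence is modest. Protocol Amendment 7 moved immunogenicity to the exploratory objectives, the Ad26 assay is run in a subset, and SAP 6.3 tests no immunogenicity hypothesis. Primary VE is unaffected, and so are VE analyses using baseline Ad26 status, which a dose after Day 1 cannot alter. The correction is still worth making because the exposure is already recorded and the remedy is small.

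**What to change.** Add the following to SAP Sections 6 and 6.3.2:

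- From the recorded COVID-19 vaccination type and date, derive a flag for each sample drawn after an Ad26-vectored COVID-19 vaccine received after Day 1.
- Mark flagged samples in the 6.3.2 tables, participant profiles and scatterplots.
- Present the Ad26 vector summaries (percentage seropositive, geometric mean, fold change from baseline) twice, with and without flagged samples.
- Label the change as made after unblinding. The SAP's amendment history dates study-level unblinding to 18 January 2023. The flag depends on recorded exposure, not on arm or assay result.

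The cost is one derived variable, one extra set of tables and slightly fewer samples in the restricted summary. No new data are needed, provided the COVID-19 product can be identified from the record. That should be possible, since SAP 3.9.2 analyses concomitant therapies by WHO drug coded terms. If the Data Presentation Specifications or the Correlates SAP already hold such a rule, a cross-reference in Section 6 would be enough.

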#### **6.1. Parameters**

The following humoral and cellular immunogenicity may be assessed by immune responses against the insert or relevant antigens from isolated HIV-1 strains using (conditional that data are available): ELISA (total IgG titers), BAMA (breadth and magnitude of binding antibody responses), IFN- $\gamma$  ELISPOT (T-cells producing IFN- $\gamma$ ) and/or ICS (T-cells expressing cytokines on a 28-color flow cytometric panel). Additional cellular and/or humoral immunogenicity analyses might be considered. Immunogenicity against the vector will be explored using an adenovirus 26 neutralization assay to assess neutralizing antibody responses against the vector.

## 6.2. Handling of Missing and/or Unquantifiable Immune Response Data

Missing immune response data will not be imputed.

Values below the limit of quantification or limit of detection will be imputed. Details per assay will be in the DPS.

## 6.3. Immune Response Analysis

No formal hypothesis on immunogenicity will be tested.

A selection of tables and figures may be produced by subgroup. Subgroups may include country, Ad26 baseline serostatus, P(r)EP use, age, BMI and race.

### 6.3.1. Immunogenicity against the insert

#### 6.3.1.1. Humoral assays

For **ELISA** assays (when available) following results may be calculated: N, geometric mean§ and corresponding 95% CI of the actual values and fold increases from baseline will be tabulated and graphically presented. §calculate the mean and corresponding 95%CI of the logx transformed values, back-transform this mean [i.e.  $x^{\text{mean}}$ ] and CI [i.e.  $x^{\text{CI}}$ ].

Actual values and fold changes from baseline are tabulated and shown as dot plots with dots for participant values, and the corresponding geometric mean and 95% CI per time point for each assay. In addition, GMT plots over time, combining the regimens in one graph (without individual participant dots) will also be created.

In the graphs, original values will be displayed on the log scale.

For **BAMA** (when available) following results will be calculated for binding antibody responses to each individual antigen and for the breadth score: N, median response and corresponding quartile range, min and max will be tabulated and graphically presented. Cumulative number of responses across the IgG/antigen classes may be tabulated.

Breadth scores are calculated from antigen-level log10 truncated Net MFI, where before applying the log10 transformation. Magnitude-breadth (MB) plots for the BAMA assay will be provided to explore the magnitude and breadth of each individual serum sample assayed. MB curves will show, for each possible MFI threshold, the fraction of antigens with MFI greater than this threshold. Weights will be applied to take into account the correlation among the antigens (more details will be specified in the DPS). The group-specific curve obtained as the average MB across all subjects in that group will be displayed. The AUC-MB is calculated as the average of the MFI over the panel of antigens.

### 6.3.1.2. Cellular assays

For **ICS** (when available) the following results will be calculated: for CD4+ and CD8+ and for each antigen (combined and separated pools): N, median, quartile range, min, max, percentage of responders and corresponding 95% CI will be tabulated for each available cytokine background adjusted percentage. Graphical presentations will be provided displaying dots for the subject values and including the median and the percentage of responders. In the graphs the actual values will be shown and the LLOQ cut-off will be visualized, the values below LLOQ will be visualized with the value imputed as LLOQ/2. In the graphs, original values will be displayed on the log10 scale.

For **ELISpot** (when available) following results will be calculated: N, median, quartiles and range of the actual values will be tabulated and graphically presented.

Tables with the corresponding descriptive statistics will be provided.

Participants profiles of the actual values over time will be graphically presented.

Actual values are shown as box plots with dots for participant values, and the corresponding median and interquartile range per time point for each assay. In addition, box plots over time, combining the regimens in one graph (without individual participant dots) will also be created. For the graphs, original values will be displayed on the log scale.

